The data manager and study coordinator will review the Dimagi platform data reports, which include logs of all texts sent, received, responded to, as well as a log of “STOP” requests. These reports will be pulled by week and by clinic. The data manager and study coordinator will provide summary data to clinic sites as well as action items (e.g., follow up with “STOP” participants to inquire if they would like to discontinue from the study, or stop their messages for short time period). Summary statistics will be provided monthly as process data for the entire study team to review.

Sites in the control arm will continue the standard of care, which will include traditional adherence counseling. Data from the EMR will be gathered for both the control and intervention site participants to include viral load and visit attendance.

At baseline, univariate analyses will be used to characterize the sample; and bivariate analysis will be employed to explore any differences between groups (e.g., differences between clinics; age categories; sex). Fisher’s Exact Test and χ^2 tests (for categorical variables) and t-tests (for continuous variables) will be used to identify demographic and behavioral factors associated with adherence and retention in care. Generalized linear models (GLMs) will be used to assess the effect of the intervention on the outcomes between the intervention and the control arm at 3 months and pre-post differences in the control arm after received the intervention at 6 months. GLMs can accommodate dependent variables with normal, binary, Poisson, and negative binomial distributions and can be adapted to incorporate random and fixed effects (generalized linear mixed models; GLMMs) to account for within-subject correlation among repeated measures over time.³¹ The generalized estimating equation (GEE) can be used to compare ‘average’ population-level response to the intervention.³² Potential confounding and effect modification by sociodemographic characteristics and location (defined by urban vs. rural residence) will be examined in exploratory analysis and these variables will be selected for inclusion in multivariable models based on statistical significance and conceptual importance. All models will account for correlation among repeated measures on individuals and within sites over time as appropriate. Inclusion of random effects for intercept and trend over time will be explored to assess subject-specific variability.

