A total of 12 clinics and up to N=600 YYALH will be enrolled in this study for evaluation purposes. Each clinic will be able to enroll up to 50 participants for a maximum total of 600 participants. We assume a 20% attrition rate, and therefore the sample size available for analysis will be N=480. Sites will be randomized to either a 3-month observation (i.e., comparison arm) or an immediate start intervention arm; at the end of the first 3-month period comparison arm sites will start the intervention for the 3 months and intervention sites will continue the intervention for an additional 3 months (6 months total). Pre-post EMR data, SMS data, and participant satisfaction data will be collected to determine efficacy, durability, maintenance and satisfaction (see expected outcomes). Rapid interim data analysis and interpretation will occur at 3 months. In Year 3, all clinics and participants (in both the initial control arm or intervention arm) will have their medical records abstracted. In addition, de-briefing interviews will be conducted with clinic staff to assess implementation outcomes. Final analysis and sustainability plan will be conducted and elaborated.

This cluster randomized control study is powered to detect 20% difference in ART adherence (>90%) among participants receiving the TXTXT intervention and the control groups. The power is calculated based on 3 levels hierarchical model design (i.e., randomization at the site level, two measures for each participant). The correlations between the participants within the site is assumed to be 0.05 and correlation within a participant is assumed to be 0.2. The proportion of participants with $\geq 90\%$ ART adherence for the control group is assumed to be 25%, 35%, 45% and 55%. The effect size is assumed to be 10%, 20% and 25%. Given Type I error rate is 0.05, using the mixed model approach, the corresponding power is listed below.³⁵ The sample size with 6 sites in each arm and 50 participants from each site would have 80% power to detect 20% difference at 3 month post baseline.

Table 2: Power (6 sites in each arm, 40 participants from each site)

		proportion of participants with $\geq 90\%$ ART adherence (Control)			
Effect Size	25%	35%	45%	55%	
10%	0.30	0.29	0.28	0.29	
20%	0.82	0.80	0.80	0.83	
25%	0.95	0.94	0.94	0.96	

Track Lessons Learned

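### Correlates of adherence and retention are to be tested without allowing for clinic; a nominal 5% test then errs about 5% to 10% of the time for participant-level factors, and more only as a factor approaches clinic level

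*Combined protocol and SAP*

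**What the plan says.** All references are to the combined protocol and SAP. Under Aim 1, Data Analysis Plan and Variables, baseline data are first described and compared between groups, with clinics, age categories and sex as examples. The plan then names Fisher's exact and chi-square tests for categorical variables, and for the rest: "t-tests (for continuous variables) will be used to identify demographic and behavioral factors associated with adherence and retention in care". No adjustment or stratification by clinic is given for any of these tests.

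The same paragraph introduces generalized linear models, mixed models and GEE for the intervention effect. Sociodemographic characteristics and urban or rural residence are to be explored as confounders or effect modifiers, and "these variables will be selected for inclusion in multivariable models based on statistical significance and conceptual importance". The next sentence deals with clustering: "All models will account for correlation among repeated measures on individuals and within sites over time as appropriate".

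Under Sample size, power calculation, and clinic scale up, the plan takes clinic clustering as given: "The correlations between the participants within the site is assumed to be 0.05".

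**The concern.** The power calculation counts clinic clustering, but the bivariate tests do not. A chi-square, Fisher or t-test takes every participant as an independent observation. If both the outcome and the factor differ between clinics, the standard error is too small and the p-value is too low.

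The sentence on correlation does not repair this, because it speaks of models and these tests are not models. The stated purpose is to identify associated factors, so significant results could be reported as correlates of adherence or retention more often than 5% of the time when no association exists. If anyone also used these p-values to screen covariates, the same excess would carry into the multivariable models.

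**Working it through.** **Inputs from the documents**
- Outcome ICC 0.05, stated within the adherence power calculation.
- Measures and within-participant correlation: "randomization at the site level, two measures for each participant" and "correlation within a participant is assumed to be 0.2".
- Clinics and size: "Table 2: Power (6 sites in each arm, 40 participants from each site", so 12 clinics with 40 analysed in each. Up to 50 per clinic are enrolled, so both sizes are shown below.
- Error rate: "Given Type I error rate is 0.05". Sidedness is not stated; two-sided is assumed.

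**Inputs not in the documents (assumed, shown as a range)**
- The ICC of each demographic or behavioral factor, from 0 (same distribution in every clinic) to 1 (constant within a clinic).
- The ICC of retention.

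**Step 1. Reproduce the plan's own figure.** The three-level inflation factor is 1 + 2 × 39 × 0.05 + 1 × 0.2 = 5.10. The effective number per arm is 6 × 40 × 2 / 5.10 = 94.1. Two-sided power for a 20-point difference (pooled variance) at control rates of 25%, 35%, 45% and 55% is then 0.826, 0.792, 0.792 and 0.826. Table 2 prints 0.82, 0.80, 0.80 and 0.83. The remaining cells agree within 2 points, except the 10-point effect at 25% (0.321 against 0.30). Table 2 therefore does rest on a site correlation of 0.05. The documents state no error rate for the bivariate tests, so there is nothing of that kind to reproduce.

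**Step 2. Actual error of an unadjusted test.** With one measurement per participant and equal clinic sizes m:

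- DE = 1 + (m − 1) × ICC of factor × ICC of outcome
- actual error = 2 × [1 − Φ(1.96 / √DE)]

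With outcome ICC 0.05:

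| Factor ICC (assumed) | DE, m = 40 | Error, m = 40 | DE, m = 50 | Error, m = 50 |
|---|---|---|---|---|
| 0 | 1.00 | 5.0% | 1.00 | 5.0% |
| 0.05 | 1.10 | 6.1% | 1.12 | 6.4% |
| 0.10 | 1.20 | 7.3% | 1.25 | 7.9% |
| 0.20 | 1.39 | 9.6% | 1.49 | 10.8% |
| 0.30 | 1.59 | 12.0% | 1.74 | 13.7% |
| 0.50 | 1.98 | 16.3% | 2.23 | 18.9% |
| 1 (constant within clinic) | 2.95 | 25.4% | 3.45 | 29.1% |

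**Step 3. Check by simulation.** Chi-square test, 12 clinics, beta-binomial outcome with ICC 0.05 and prevalence 35% or 50%, binary factor with prevalence 50%, 10,000 replicates per setting. With m = 40, the two prevalences gave 5.1% and 5.0% at factor ICC 0, 9.3% and 9.6% at 0.20, 15.9% and 15.8% at 0.50, and 25.8% and 25.3% at 1. With m = 50 and factor ICC 1 they gave 29.8% and 29.5%. The formula holds. Only the chi-square case was simulated.

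**Step 4. Retention.** Its ICC is not given, so the outcome ICC is varied with m = 40:

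| Outcome ICC (assumed) | Error at factor ICC 0.20 | Error at factor ICC 1 |
|---|---|---|
| 0.01 | 5.9% | 9.6% |
| 0.02 | 6.8% | 14.2% |
| 0.10 | 14.2% | 37.6% |

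**The case against.** The strongest reply is that the matter is small. The sentence at issue concerns demographic and behavioral factors, which vary between people in the same clinic, so most sit in the upper rows of the first table. The tests follow a description of the sample and no Aim 1 hypothesis depends on them. If they are meant as description only, labelling them so and reporting no p-values would be enough. All of this stands, and it keeps the point minor.

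A reader might infer that these tests have a false-positive rate of about 25%. The documents do not support that as a general rate. It needs a factor identical for everyone in a clinic. The Innovation section mentions comparing Ryan White with other clinics, but attaches no test to it. Location in the analysis plan is the participant's residence; it may come close to a clinic-level factor, but it is examined in the exploratory work for the multivariable models.

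A reader might also infer that the tests decide which covariates enter the models. The plan does not say so. Selection rests on significance together with conceptual importance, and the sentence stands next to the one requiring models to allow for site, so a model-based p-value is a natural reading. Use of the unadjusted tests is possible, because the source of the significance is not stated.

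Nor does the text call for a warning about baseline p-values between arms: its example groups are clinics, age categories and sex.

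**Conclusion.** The gap is real and minor. As written, the tests for correlates of adherence and retention ignore clinic, and the clustering sentence does not reach them. For participant-level factors with an assumed ICC of 0 to 0.20, a nominal 5% test has an actual error of 5.0% to 9.6% with 40 per clinic. It is about 16% at a factor ICC of 0.50, and about 25% (29% with 50 per clinic) only at the limit of a factor constant within a clinic.

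These figures rest on the plan's adherence ICC of 0.05, equal clinic sizes, a two-sided test and one measurement per participant. For retention they are illustrative only.

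A reader might take this as a threat to the main result. It is not directly one: the 3-month comparison between arms is to be made with models that the plan says will allow for correlation within sites.

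**What to change.** In Data Analysis Plan and Variables, replace the Fisher, chi-square and t-tests for correlates with clinic-adjusted analyses. Any of these would do:
- logistic or linear mixed models with a clinic random intercept;
- GEE clustered on clinic with a small-sample correction for 12 clinics;
- Rao-Scott-adjusted tests.

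Report each association as an estimate with a confidence interval. State also that covariate selection does not use unadjusted p-values.

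The cost is a change of SAP wording and a little more analysis work on the same data. Intervals will be slightly wider. As a guide, at a factor ICC of 0.20 with 40 per clinic the width grows by about 18% (√1.39 = 1.18).

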Retention will be facilitated through obtaining contact information for the participant during the initial stages of the enrollment process. To minimize participant and staff burden, the follow-up visits can be conducted virtually. Participants will be sent a personalized link to complete the follow-up survey via REDCap. Of note, there will not be financial reimbursement for participation in the

intervention as the goal of the project is to understand how TXTXT will work in the “real world” and inform wide scale routine implementation. Prior studies by Drs. [name], [name], and [name] with vulnerable adolescent and other marginalized populations have maintained >80% retention. We will employ best practices in participant retention including: 1) collecting extensive locator information (multiple addresses/emails, phone numbers, social media profile names, etc.); 2) identification and discussion of difficult-to-reach participants and potential solutions during weekly team meetings; and 3) maintaining flexibility with mode of follow-up (e.g., in person options as well as internet based). The investigative team and participating clinic staff will review the study team’s retention plans and will be asked for guidance on how to best keep YYALH engaged in the study for at least 6 months. No financial incentives will be provided to youth participating in the TXTXT intervention trial (Aim 1). At 3 months, 6 months, and 12 months post baseline, electronic medical record (EMR) data from participating clinics will be used to determine viral load; retention in care will be assessed for up to 12 months post baseline.

STUDY DESIGN AND DATA ANALYSIS

Study participation summary

1. 12 participating clinics randomized 1:1 into intervention or comparison arm
2. 50 participants at each clinic enrolled and complete baseline survey; baseline EMR data pulled
3. Participants at intervention clinics begin TXTXT after baseline survey and continue for 6 months
4. All participants complete a 3-month survey
5. Participants at comparison clinics begin TXTXT after 3-month survey and continue for 3 months
6. All participants complete a 6-month survey; 6-month EMR data pulled
7. TXTXT intervention stops at 6 months post baseline for all participants
8. 12-month EMR data pulled

Timepoint	Who	What	Data collected
zero	12 participating clinics	Randomized 1:1 intervention: comparison arm	

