In order to assess feasibility, acceptability and satisfaction of the intervention we will use descriptive statistics using a combination of objective (e.g., rates of participation, intervention completion) and subjective measures (e.g., reported satisfaction, acceptability). In order to characterize adherence and retention in care throughout the course of the study, Kaplan-Meier survival curves will be used to measure time to adherence and retention, and Cox proportional hazard ratios will be used to assess whether individual-level factors are associated with shorter mean time to outcome. To measure reach of the intended participants, we will compare the study sample to those available in the sampling frame (proportion of those enrolled to those eligible). To measure adoption of clinic partners, we will evaluate the number of clinic partners who propose to continue with text messaging as adherence support post study (proportion of clinics who propose to continue TXTXT post study to total clinics). Satisfaction and acceptability will be measured by standard quantitative scales, summary total scores will be evaluated to determine whether or not ≥90% ratings were achieved.

Outcome definitions

Medication adherence: greater than or equal to 90% on self-reported visual analog scaler (non-adherence categorized at less than 90%)

Retention in care³³: two visits 90 days apart in the past year will be considered retained in HIV care

Viral suppression³⁴: VL < 200 copies/mL will be considered virally suppressed

Sample size, power calculation, and clinic scale up

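### No small-sample method is named for comparing 6 with 6 clinics: z inference would run at about 8% to 10% instead of 5%, and a test that holds 5% has less than the stated 80% power

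*Combined protocol and SAP*

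**What the plan says.** The Study participation summary has "12 participating clinics randomized 1:1 into intervention or comparison arm". The 3-month outcomes are binary under Outcome definitions: adherence of at least 90% on the self-report scale, and suppression, where "VL < 200 copies/mL will be considered virally suppressed".

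For the arm comparison, the Aim 1 section Data Analysis Plan and Variables names generalized linear models, notes that they can be extended with random effects, and adds that "The generalized estimating equation (GEE) can be used to compare" average responses. On clustering it says: "All models will account for correlation among repeated measures on individuals and within sites over time as appropriate". The t-tests in that section are for factors associated with adherence and retention, not for the arm effect.

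Sample size, power calculation, and clinic scale up gives the power basis: "Given Type I error rate is 0.05, using the mixed model approach". It states that 6 sites per arm "would have 80% power to detect 20% difference at 3 month post baseline", and it caps recruitment: "Each clinic will be able to enroll up to 50 participants for a maximum total of 600 participants".

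**The concern.** With 6 clinics per arm, the between-clinic variance that drives the standard error is estimated on 10 degrees of freedom. Large-sample (z) p-values from GEE or a mixed model treat that variance as known. The uncorrected sandwich and maximum likelihood also tend to underestimate it. Valid methods for few clusters exist, but the plan chooses none, so tests of different true size remain open after the data are seen.

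Two stated figures are at stake, the 5% type I error and the 80% power. If z is used, an ineffective programme is declared effective more often than one time in 20. If a valid test is used, the trial is less sensitive than stated. The plan intends a favourable result to support wider scale-up.

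**Working it through.** **Inputs (Sample size section):** 12 clinics, 6 per arm; 40 analysed per clinic (50 less 20% attrition), so 240 per arm; ICC 0.05; within-participant correlation 0.2; two measures per participant; control adherence 25, 35, 45 or 55%; difference 20 points; alpha 0.05, taken as two-sided.

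**1. Reproduce Table 2.** The three-level variance factor is (1 + 0.2 + 2 × 39 × 0.05)/2 = 5.1/2 = 2.55. Effective n per arm is 240/2.55 = 94.1. For 35% against 55%, the unpooled SE is √[(0.35 × 0.65 + 0.55 × 0.45)/94.1] = 0.0710, and z power is Φ(0.20/0.0710 − 1.960) = 0.80.

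**2. Replace z by t with 10 df, same SE** (noncentral t, cut-off 2.228).

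**3. One 3-month measure.** The variance factor is 1 + 39 × 0.05 = 2.95 and effective n per arm is 240/2.95 = 81.4.

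| Power for 20 points | 25% | 35% | 45% | 55% |
|---|---|---|---|---|
| Table 2 | 0.82 | 0.80 | 0.80 | 0.83 |
| Two measures, z, unpooled | 0.837 | 0.804 | 0.804 | 0.837 |
| Two measures, z, pooled | 0.820 | 0.788 | 0.788 | 0.820 |
| Two measures, t(10), unpooled | 0.755 | 0.719 | 0.719 | 0.755 |
| Two measures, t(10), pooled | 0.737 | 0.701 | 0.701 | 0.737 |
| One measure, t(10), unpooled | 0.694 | 0.656 | 0.656 | 0.694 |
| One measure, t(10), pooled | 0.675 | 0.638 | 0.638 | 0.675 |

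The z rows match Table 2 within 2 points; the t(10) rows miss it by 6 to 10 points. Over the whole table, 11 of 12 cells reproduce with z. The exception is 10 points at 25% control, computed as 0.32 against 0.30. Simulating the clinic-level t-test on one measure gives 0.65 to 0.69. If all 50 per clinic were analysed, two-measure t(10) power would be 0.72 to 0.77.

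**4. Size of a nominal 5% z test, equal clinics.**
- Unbiased between-clinic variance: 2 × P(t₁₀ > 1.960) = 7.8%.
- Uncorrected sandwich: it divides by 6 instead of 5 within each arm, so the effective cut-off is 1.960/√(6/5) = 1.789, and 2 × P(t₁₀ > 1.789) = 10.4%.

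Simulation with beta-binomial counts (12 × 40, ICC 0.05, one measure, no effect, rates 25 to 55%, 200,000 runs each) agrees: clinic-level z about 8%, uncorrected sandwich z about 10.4%, clinic-level t(10) 5.0 to 5.1%. A logistic random-intercept model fitted by maximum likelihood with Wald z gave 9.5 to 10.1% (6,000 fits per rate). A separate run of 1,200 fits at 35% gave 8.7% (simulation SE 0.8 points). Using t(10) in that same model still gave 6.1 to 6.7%.

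**5. Unequal clinic sizes.** The plan gives no size distribution. Assuming sizes uniform on 30 to 50 or 20 to 50, which respects the cap, the sandwich z size is at most about 10.9%, against 10.4% for equal sizes. The clinic-level t(10) test stays at 5.0%.

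**6. Interval width.** A z-based 95% interval would need to be 2.228/1.960 = 1.14 times as wide with an unbiased variance, or 1.14 × √(6/5) = 1.25 times with the uncorrected sandwich.

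**The case against.** The strongest reply is that the plan never says z. An analyst following it could choose a valid small-sample test, because the clustering sentence leaves room for one. That stands. A reader might infer that the trial will run at 8% to 10%, or that the plan ignores clustering, and the documents support neither. They commit to handling correlation within sites and leave the method open. The 8% to 10% therefore applies only if z inference is used. The power finding does not need that condition, because Table 2 rests on z and any test that holds 5% falls short of it.

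A reader might also expect unequal recruitment to push the sandwich size well beyond 10%. Sizes varied enough to do that (coefficients of variation of 0.4 to 0.5 around a mean of 40) put many clinics above 50, which the cap rules out. Within the cap the effect is slight.

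Nor does the sentence on covariate selection show that the primary test is data-driven. It says that confounders "will be examined in exploratory analysis and these variables will be selected for inclusion in multivariable models based on statistical significance and conceptual importance", which places the screening in exploratory work.

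Finally, the logistic mixed-model figure is less precise than the others. The two simulations, 8.7% and 9.5 to 10.1%, are compatible within error and both lie in the stated range. At an ICC of 0.01 and a 35% rate that model gave 7.3%, so the range is specific to the plan's ICC of 0.05.

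**Conclusion.** The point holds. No method suited to 12 clusters is named, and the stated combination of alpha 0.05 and 80% power for 20 points is not delivered. With z inference the true size is about 8% to 10%. With a valid t(10) test, power is 0.70 to 0.76 (pooled to unpooled variance) on the plan's two-measure inputs, or about 0.64 to 0.69 on the single 3-month measure.

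These figures assume 40 analysed per clinic and an ICC of 0.05; the power figures assume equal clinic sizes. The higher power range also keeps the credit for two measures. The plan does not say which two are meant, and the comparison arm starts the intervention after 3 months, so that credit needs justifying. The power figures concern adherence, the only outcome powered. The size figures barely change across the rates tried, so the gap applies to viral suppression too. The design itself stands; the inference and the power statement should be corrected before analysis.

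**What to change.** In Data Analysis Plan and Variables, for each 3-month primary outcome, name one primary analysis with clinic as the cluster and a small-sample method that holds 5% with 12 clusters. Options:

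- A clinic-level t-test with 10 df, which held 5% with equal and unequal clinic sizes.
- A permutation test over the allowed allocations (924 if unrestricted). On clinic proportions it was slightly conservative with equal sizes, at 4.1%.
- A bias-corrected sandwich with a t reference, stating the correction and how it behaves with unequal clinic sizes.

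Replacing z by t(10) in a maximum-likelihood logistic mixed model should not be assumed sufficient.

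In the Sample size section, restate power for the analysis chosen: about 0.64 to 0.69 for a single 3-month measure, or about 0.70 to 0.76 only if the two-measure model and its correlation assumptions are kept and justified.

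The cost is wording and standard software, with no new data or participants. The downside is that stated power falls below 80%.
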